## **7.8 Efficacy Analysis**

Efficacy analyses will be performed on the FAS analysis set, and individual data will be listed.

Unless specified otherwise, only 95% confidence interval (CI) will be presented within sex group. No inferential analysis for comparison between sex group will be performed.

As described in section 7.1, efficacy results will be presented separately in the following segments by sex group (male and female plus total):

- Treatment Phase: ENANTONE treatment
- Follow-up Phase:
  - participants that received ENANTONE treatment in the treatment phase
  - If data permit, data from non-ENANTONE GnRHa treatment; as well as data after completion of non-ENANTONE GnRHa treatment

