8.0 RATIONALE AND BACKGROUND

Precocious puberty refers to appearance of secondary sexual characteristics in boys before 9 years and girls before 8 years [1]. Children with CPP have premature secretion and release of GnRH in the hypothalamus, activating secretion of gonadotropin by the pituitary gland, promoting development of the gonads and secretion of sex hormones, resulting in development of internal and external genital organs and appearance of secondary sexual characteristics [1]. Treatment goals include hormonal suppression, cessation of development of secondary sex characteristics, halting or preventing menarche, and preservation of adult height [1][2]. If left untreated, children with CPP can also face psychological challenge resulting from premature physical maturation that contrasts with their immature emotional development [2].

GnRHa have been the standard of care for CPP [1]. Continuous exposure to GnRHa desensitizes pituitary gonadotropin receptors and suppresses LH and FSH secretion [2].

ENANTONE is a GnRHa widely used in the treatment of CPP. It was approved for CPP indication in China in 1998 at the dose of 30-90 µg/kg body weight subcutaneously administration every 4 weeks. However, recent clinical studies demonstrated that administration of leuprorelin acetate at lower than 90 µg/kg body weight cannot achieve optimal pituitary desensitization in many patients. If incomplete suppression is operative during treatment, GnRHa administration may exacerbate disease progression and bone age increase, impairing long-term outcome [3]. The dose greater than 90 µg/kg body weight was recommended in CPP treatment guideline issued in 2010 by the Ministry of Health of China and Consensus on Diagnosis and Treatment of Central Precocious Puberty (2015) [4][5].

In 2013, CFDA approved the new dose of leuprorelin acetate at 30-180 µg/kg body weight, SC, every 4 weeks [6]. The approval was based on results from the clinical trials of leuprorelin acetate conducted in US and Europe and a retrospective study in Japan [7][8]. There is a lack of safety and effectiveness data of leuprorelin acetate long term use in China. This retrospective, medical chart review study is designed to evaluate and compare descriptively the effectiveness and safety of high dose (≥ 90 µg/kg up to 180 µg/kg) and low dose (< 90 µg/kg down to 30 µg/kg) leuprorelin acetate in China.

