9.0 RESEARCH QUESTION AND OBJECTIVES

The goal of this study is to evaluate the safety and effectiveness of leuprorelin acetate in CPP treatment in China.

Objective 1: To describe the safety of high dose leuprorelin acetate ($\geq 90 \mu\text{g}/\text{kg}$ up to $180 \mu\text{g}/\text{kg}$) and low dose leuprorelin acetate ($<90 \mu\text{g}/\text{kg}$ down to $30 \mu\text{g}/\text{kg}$) in CPP treatment of at least 9 continuous months of ENANTONE

Objective 2: To describe the long term effectiveness of high dose leuprorelin acetate ($\geq 90 \mu\text{g}/\text{kg}$ up to $180 \mu\text{g}/\text{kg}$) and low dose leuprorelin acetate ($<90 \mu\text{g}/\text{kg}$ down to $30 \mu\text{g}/\text{kg}$) in CPP treatment of at least 9 continuous months of ENANTONE

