10.7.1 Analysis Sets

A statistical analysis plan (SAP) will be developed prior to releasing the study data to statisticians for analysis. Unless otherwise specified, statistical analyses will be performed using SAS © version 9.2, or later. Unless otherwise specified, data analyses and tabulations will be by dose level (high or low) and all subjects combined; with supportive analyses stratified by sex. Additional stratification variables may be identified in the SAP.

All enrolled subjects who are enrolled will be included in the Safety Analysis Set and the Full Analysis Set (FAS).

If 5% or more of the FAS set are found to have violated some of the following study criteria then repeat analysis will be performed on the Per Protocol Set, defined as subjects as follows:

- Duration of treatment of at least 9 continuous months of leuprorelin acetate (ENANTONE), with evaluation

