10.7.2 Analysis of Demographics and Other Baseline Characteristics

Demographic and baseline characteristics will be summarized for each of the dose level groups (high, low dose). Descriptive statistics (eg, N, mean, standard deviation, median, minimum, and maximum) will be generated for continuous variables (eg, age, height, weight, etc.) and the number and percentage of subjects within each category will be presented for categorical variables (eg, sex). Additional categories (eg, BMI intervals) maybe specified in the SAP. Medical history, concurrent medical conditions and concomitant medications will be tabulated. Descriptive statistics will also be determined for duration of time on treatment and follow up by dose level and by demographic categories (eg, male, female) within dose level.

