10.9 Limitations of the Research Methods

This is an observational study, where the assignment to the dose level of leuprorelin acetate is at the discretion of the treating physician, which may also vary according to the patient's body mass. Unlike clinical trials where treatment assignment is randomized to reduce physician bias, no randomization is used in the dose selection, and certain biases and confounding influences are inevitably present in the data to be analyzed. Subgroup analysis to evaluate the effect of dose on study outcomes will be performed for selected parameters.

This study is not statistically powered for any hypothesis testing, and all outcomes will be summarized using descriptive statistics. Since this study is observational and data will be collected as part of routine clinical practice and outcomes will be reported on the available data. No imputation of missing data will be conducted.

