## **4.0 OBJECTIVES**

### **4.1 Primary Objectives**

The goal of this study is to evaluate the safety and effectiveness of leuprorelin acetate in central precocious puberty (CPP) treatment in China.

Objective 1: To evaluate the safety of high dose leuprorelin acetate ( $\geq 90 \mu\text{g}/\text{kg}$  up to  $180 \mu\text{g}/\text{kg}$ ) and low dose leuprorelin acetate ( $< 90 \mu\text{g}/\text{kg}$  down to  $30 \mu\text{g}/\text{kg}$ ) in CPP treatment of at least 9 continuous months of ENANTONE

Objective 2: To evaluate the long-term effectiveness of high dose leuprorelin acetate ( $\geq 90 \mu\text{g}/\text{kg}$  up to  $180 \mu\text{g}/\text{kg}$ ) and low dose leuprorelin acetate ( $< 90 \mu\text{g}/\text{kg}$  down to  $30 \mu\text{g}/\text{kg}$ ) in CPP treatment of at least 9 continuous months of ENANTONE

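### The SAP tabulates baseline, exposure and effectiveness by sex instead of dose, so Objective 2 gets no high-dose or low-dose response rate, and SAP 7.13 does not clearly say so

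*SAP*

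**What the plan says.** **Objectives.** Protocol 9.0 has "Objective 2: To describe the long term effectiveness of high dose leuprorelin acetate" and goes on to name low dose. SAP 4.1 keeps this under its primary objectives: "Objective 2: To evaluate the long-term effectiveness of high dose leuprorelin acetate", again followed by low dose.

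**Protocol analysis plan.** Section 8.0 says the study "is designed to evaluate and compare descriptively the effectiveness and safety of high dose" and low dose. Section 10.7.1 sets the default: "Unless otherwise specified, data analyses and tabulations will be by dose level (high or low) and all subjects combined", with sex stratification as supportive. Section 10.7.2 is explicit: "Demographic and baseline characteristics will be summarized for each of the dose level groups (high, low dose", and "Descriptive statistics will also be determined for duration of time on treatment and follow up by dose level". Section 10.9 adds: "Subgroup analysis to evaluate the effect of dose on study outcomes will be performed for selected parameters". For the primary effectiveness outcome, 10.7.3 uses dose in the CMH test and gives the Clopper-Pearson interval for all subjects and by sex.

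**SAP.** Section 7.1 makes male, female and total the default grouping, and 7.4 (baseline) names no other. Section 7.7 tabulates duration by sex. Section 7.8 says "efficacy results will be presented separately in the following segments by sex group (male and female plus total", and 7.8.1 to 7.8.3 add no dose grouping. Section 7.11 still analyses safety by high dose, low dose and overall. Section 7.13 says the protocol expected enough subjects to compare the doses, that analyses of that kind are no longer feasible, and that the CMH test is therefore omitted.

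**The concern.** The protocol makes dose the main reporting factor and sex a supportive one. The SAP reverses this for everything except safety and gives no explicit reason for the reversal. The dose-specific half of a primary objective would go unanswered, and a reader of the report would not find that plainly declared.

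There is a second consequence. Safety would appear by dose with no baseline or exposure table beside it to show how the two dose groups differ. Protocol 10.9 itself warns that the physician chooses the dose, that it may vary with body mass, and that confounding is unavoidable. By-dose safety rates are hard to read without those tables.

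**Working it through.** **1. Groupings side by side**

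| Content | Protocol | SAP |
|---|---|---|
| Objective 2 | each dose (9.0) | each dose (4.1) |
| Default tabulation | dose and combined; sex supportive (10.7.1) | male, female, total (7.1) |
| Baseline | dose (10.7.2) | 7.1 default applies (7.4) |
| Treatment and follow-up duration | dose, and demographics within dose (10.7.2) | sex (7.7) |
| Effectiveness | 10.7.1 default; CMH by dose; exact CI for all subjects and by sex (10.7.3) | sex plus total (7.8 to 7.8.3) |
| Safety | dose and overall (10.7.4) | dose and overall (7.11) |

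Baseline and exposure are the clearest departures, because 10.7.2 names dose expressly. For effectiveness, 10.7.3 does not itself name a by-dose exact interval. That requirement rests on Objective 2 and on Protocol 8.0, 10.7.1 and 10.9.

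**2. Reproducing Protocol 10.5**

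Inputs: 300 subjects split evenly (150 per dose), response rates of 75% (low) and 85% (high), 95% confidence.

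- Wald half-width = 1.96 × √(p(1−p)/n). Low: 1.96 × √(0.75 × 0.25/150) = 6.9 points. High: 1.96 × √(0.85 × 0.15/150) = 5.7 points.
- Exact half-widths: 7.2 points (112/150 and 113/150) and 6.0 to 6.1 points (128/150 and 127/150).
- Odds ratio = (0.85/0.15)/(0.75/0.25) = 1.89. Woolf SE of the log odds ratio = √(1/112.5 + 1/37.5 + 1/127.5 + 1/22.5) = 0.296, giving a 95% CI of 1.06 to 3.38.

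The stated margins of about 7% and 6%, and the lower bound above 1.0, all reproduce for 300.

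**3. The same quantities at 100 subjects**

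The documents give no dose split for 100, so every split here is an assumption. At 50 per dose the SE becomes √(1/37.5 + 1/12.5 + 1/42.5 + 1/7.5) = 0.513, and the odds-ratio CI is 0.69 to 5.17. At assumed low/high splits from 10/90 to 90/10, the lower limit runs from 0.31 to 0.69. Dropping between-dose inference is therefore reasonable.

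**4. Whether within-dose description remains possible**

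Clopper-Pearson limits are the 2.5% quantile of Beta(x, n−x+1) and the 97.5% quantile of Beta(x+1, n−x). Half-width is half the total width; the intervals are asymmetric.

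| Group (assumed size) | x/n | Exact 95% CI | Half-width (points) |
|---|---|---|---|
| All subjects | 80/100 | 70.8–87.3% | 8.3 |
| 80 in a dose group | 60/80 | 64.1–84.0% | 10.0 |
| | 68/80 | 75.3–92.0% | 8.4 |
| 50 in a dose group | 37/50 | 59.7–85.4% | 12.9 |
| | 38/50 | 61.8–86.9% | 12.6 |
| | 42/50 | 70.9–92.8% | 11.0 |
| | 43/50 | 73.3–94.2% | 10.5 |
| 20 in a dose group | 15/20 | 50.9–91.3% | 20.2 |
| | 17/20 | 62.1–96.8% | 17.3 |
| 10 in a dose group | 8/10 | 44.4–97.5% | 26.5 |
| 5 in a dose group | 4/5 | 28.4–99.5% | 35.6 |

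A percentage with an exact interval can be computed at any split. It is useful at 50 per dose, weak at 20 and uninformative at 10 or fewer.

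**The case against.** The strongest reply is that SAP 7.13 already discloses the change. It refers in the plural to analyses that compare the doses, and Protocol 8.0 treats description as a form of comparison, so 7.13 could be read as dropping by-dose effectiveness tables with the CMH test as the named instance. That reading is possible, so the fault is unclear disclosure, not total silence. But the only consequence 7.13 states is omission of the CMH test, it mentions neither baseline nor exposure, and by-dose safety survives in 7.11.

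Other points on that side:

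- **Protocol 10.7.3 specifies the exact interval for all subjects and by sex, and the SAP follows it.** True, and it makes the effectiveness part less explicit than the 10.7.2 part. It does not remove dose from Objective 2. Protocol 10.9 covers selected parameters only, so it is supporting evidence and no more.
- **By-dose safety in 7.11 may be carried over from Protocol 10.7.4,** since 7.11.1 sorts events by total, male and female. The documents do not settle this, but as written 7.11 is by dose.
- **Baseline weight may be missing for some subjects.** It is not among the records listed in inclusion criterion 4. However, criterion 2 already requires each subject to be placed in a dose range, and 7.11 needs the same grouping.
- **Small cells and confounding.** Both stand. By-dose cells in the 3-month windows may be thin, and adjacent unadjusted columns invite informal comparison. These call for labelling the results, not for omitting them.

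**Conclusion.** The concern holds. As written, the SAP produces no high-dose or low-dose response rate for a primary objective that it retains, and no baseline or exposure table by dose although Protocol 10.7.2 asks for both. SAP 7.13 justifies losing the comparison but does not clearly say that within-dose description is lost too.

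Confidence is high on the groupings, which can be read directly from the text. How informative the missing rates would be depends on the dose split, which is not given for 100 subjects. The plan should be corrected before analysis. Pooled and by-sex effectiveness results remain valid and are not affected.

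**What to change.** 1. **SAP 7.8.1 and 7.8.2:** add descriptive n, percentage and Clopper-Pearson 95% CI by dose group, using the Protocol 10.1.2 definition, and overall, with no between-dose test. Keep the by-sex tables. If a dose group is very small, still show the figures and note that they are uninformative.
2. **SAP 7.4 and 7.7:** add dose-group columns, as Protocol 10.7.2 asks.
3. **SAP 7.13:** say exactly which by-dose analyses are omitted. If items 1 and 2 are adopted, that is the CMH test and its odds ratio. If they are not, state openly that by-dose description of effectiveness, baseline and exposure is dropped and that Objective 2 is not answered by dose.
4. **SAP 6.0 (optional):** note that the Protocol 10.5 margins and odds-ratio statement were for 300 and do not carry over to 100. Section 6.0 does not repeat those figures, so this is clarification only. Any half-widths given should label the dose split as an assumption.

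No change to 7.11 or 7.11.1 is needed for this point.

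**Cost:** SAP wording and extra table columns. No new data are needed, because first dose and Baseline weight already define the groups. The downsides are wide intervals if one dose group is small and the risk of informal comparison between columns. The disclosure-only route in item 3 costs one sentence but leaves Objective 2 unanswered by dose.

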### **7.8.1 Primary Efficacy Endpoint(s)**

The primary effectiveness outcome, percentage of subjects who have regression or no progression (i.e. response to treatment) in Tanner staging at the end of ENANTONE treatment (i.e. the last observation in the ENANTONE treatment phase) will be analyzed using an exact method. The 95% CI for the regression or no progression responder will be determined using Clopper-Pearson exact method. Similar analysis as described above will be performed at 3-month intervals from the initiation of ENANTONE treatment. Additional time intervals maybe utilized as fitting the data.

A Tanner Stage of 5 is satisfied when both evaluations for Tanner scoring are V; specifically, breast development and pubic hair for females and genital development and pubic hair for males.

Where applicable, similar summaries, using the appropriate baseline, will be presented for the follow-up phase at 3-month intervals.

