10.5 Study Size

Approximately 300 subjects will be enrolled into the study from multiple centers across China, as required by the CFDA. Within each site, eligible subjects will be enrolled until the site's subject quota has been reached. The above sample size, if evenly split between low dose and high dose, will provide 95% confidence intervals (CIs) for the primary effectiveness variable with margins of error of approximately 7% and 6% if the observed effectiveness rates are 75% and 85%, respectively for low and high doses. Furthermore under these same assumptions a 95% CI for the odds ratio would have a lower bound >1.0, suggesting greater effectiveness for subjects treated with the high dose.

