10.7.3 Effectiveness Analysis

Any inferential statistical analysis resulting in p-values will be reported for the purpose of identifying notable findings rather than any formal test of statistical significance. Unless specified otherwise, all point estimates will be estimated alongside a companion 95% CI.

The primary effectiveness outcome, percentage of subjects who have regression or no progression (ie, response to treatment) in Tanner staging at the end of the ENANTONE Treatment Phase will be analyzed using a Cochran-Mantel-Haenszel (CMH) test with sex as

strata variable and dose (high, low) as independent variable. The adjusted odds ratio and 95% CI will be provided from the CMH test along with two-sided p-value. The 95% CI for the percent will also be determined using Clopper-Pearson exact method, unadjusted for sex, will be provided for overall responder and for each sub-response (regression/ no progression) for all subjects and by sex. If the final data are incompatible with the above analyses, then another method, such as ordinary percentages with 95% CIs (example using Wald type CIs), may be used.

Additional CMH analyses with adjustment by other demographic variables may be performed where necessary. If the data in the treatment period permits, similar analysis as described above will be performed at year intervals from the initiation of treatment, ie, Year 1, Year 2, etc.

The above analyses methodology will be also applied to the following effectiveness outcomes, at the end of the treatment phase and at year intervals, if appropriate:

- Percentage of patients with LH suppression
- Percentage of patients with FSH suppression
- Percentage of patients with estradiol or testosterone level suppression to prepubertal level
- Percentage of patients with a decrease from baseline in the ratio of bone age to chronological age
- Percentage of patients with an increase from baseline in predicted adult height

Change from baseline for BMI at end of treatment phase will be analyzed. This analysis will also be performed at each year interval, as permitted by available data and where applicable, of the treatment phase.

The above analysis will be used for the following quantitative variables, with associated baseline value as covariate:

- Change from baseline in BMI during the follow up phase, at yearly intervals, with end of treatment phase BMI as baseline
- Change from baseline in BMD, at end of treatment phase and at yearly intervals

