### **4.4 Study Design**

This observational retrospective study will evaluate the long-term safety and effectiveness of ENANTONE (leuprorelin acetate) for the treatment of CPP.

The protocol was written to include approximately 300 patients with CPP, treated with ENANTONE for at least 9 continuous months, and who initiated and received the last dose of treatment during the index period (from 1 September 1998 to 30 September 2018). With the approval of China's Center for Drug Evaluation the study was then modified to collect information from only 100 subjects. Patients who were treated with other GnRHs (including generic leuprorelin acetate) after the 9-month treatment with ENANTONE could be enrolled into the study. At each clinical site, sequential eligible patients were to be enrolled until the site's patient quota has been reached. Medical records of enrolled patients were collected and reviewed.

Study participants were expected to have met inclusion criteria, including the following key items:

[figure not shown]
- Subjects with diagnosis of idiopathic CPP
- Subjects treated with leuprorelin acetate (ENANTONE) for at least 9 continuous months of therapy with either a stable dose of high dose ( $\geq 90 \mu\text{g}/\text{kg}$  up to  $180 \mu\text{g}/\text{kg}$ ) or low dose ( $< 90 \mu\text{g}/\text{kg}$  down to  $30 \mu\text{g}/\text{kg}$ ).
- Subjects initiated and completed treatment during the index period from 1 September 1998 to 30 September 2018

- Subjects who have the following information prior to initiation of ENANTONE and at least one record of each of the following parameters at the end of ENANTONE treatment in the medical records: Tanner staging, estradiol or testosterone level, and FSH and LH level. The subject should have at least one record of bone age prior to the initiation of GnRHa therapy with ENANTONE to support the diagnosis of CPP. In addition, the subject should have at least one record of bone age during treatment with ENANTONE.

Prior to ENANTONE treatment initiation, all relevant data (specified in Protocol Section 10.2.3.1), including data pertaining to the diagnosis of CPP will be collected at all available time points. Baseline values were defined as the measurement(s) just prior to the initiation of ENANTONE treatment.

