#### 7.1.1 Study Definitions of Baseline and Change from Baseline

Baseline, for the ENANTONE period, is defined as the last non-missing measurement prior to the first dose of ENANTONE treatment. Unless specified otherwise, baseline values for variables related to CPP will be limited to values collected no more than 3 months (93 days), inclusive, prior to the first dose of ENANTONE.

The change from baseline will be calculated for the treatment period by subtracting the baseline values from the individual post-baseline values. If either the baseline or post-baseline value is missing, the change from baseline is set to be missing as well.

Data from the follow-up period after completion of treatment period, will be analyzed separately and the baseline for the follow-up period will be defined as the first non-missing measurement after the last dose of GnRHa treatment (with either ENANTONE or another GnRHa).

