## **7.13 Changes in the Statistical Analysis Plan**

The statistical analysis in the protocol anticipated sufficient subject numbers to permit the comparing of Low and High dose levels of ENANTONE. At the time of finalizing the SAP it was determined that these types of analyses wouldn't be feasible. Therefore, the proposed Cochran-Mantel-Haenszel test will be omitted.

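### SAP 7.8.1 reports an unchanged Tanner stage as response every 3 months from Month 3, when a high rate can be expected without any drug effect

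*SAP*

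**What the plan says.** SAP 7.8.1 defines the primary effectiveness outcome as the "percentage of subjects who have regression or no progression (i.e. response to treatment) in Tanner staging at the end of ENANTONE treatment". It is taken at the last observation in the treatment phase, with a Clopper-Pearson 95% interval for the combined responder. A child at the same stage as at baseline is a responder, and the time between the two records plays no part. The section then adds: "Similar analysis as described above will be performed at 3-month intervals from the initiation of ENANTONE treatment".

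SAP Table 1 (section 7.1.3) sets Month 3 at Day 91 (window Day 46 to 135) and Month 6 at Day 182 (window Day 136 to 225). If a window holds several records, the one nearest the target day is used. Under SAP 7.1.1, baseline values for CPP variables are "limited to values collected no more than 3 months (93 days), inclusive, prior to the first dose of ENANTONE".

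Protocol 10.7.3 was different on two counts. First, data permitting, "similar analysis as described above will be performed at year intervals from the initiation of treatment, ie, Year 1, Year 2, etc". Second, it asked for separate exact intervals for each sub-response, regression and no progression. SAP 7.8.1 specifies an interval only for the two combined.

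SAP 7.13 records one change, that comparing the dose levels is not feasible: "Therefore, the proposed Cochran-Mantel-Haenszel test will be omitted". It mentions neither the move to 3-month repeats nor the loss of the separate intervals.

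Eligibility (SAP 4.4) limits the population to "Subjects treated with leuprorelin acetate (ENANTONE) for at least 9 continuous months of therapy", with a Tanner record before treatment and one at its end.

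**The concern.** A tie counts as success, so the chance of scoring as a responder without any drug effect depends on how long the child was watched. Over a short enough interval most children will not have changed stage, treated or not. Yearly repeats limit the problem; a first repeat centred on Day 91 exposes it.

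No comparison offsets this. With the dose comparison dropped, the Tanner result is a single-group percentage, and nothing in the study shows what an ineffective treatment would score. The protocol's split would at least have shown how much of the response was regression and how much was a tie, but the SAP no longer specifies it.

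At stake is how the response tables are read. Month 3 and Month 6 rates would appear under the same label as later ones, in a study whose results go to the regulator to justify long-term use (Protocol 13.0).

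**Working it through.** **1. The plan's own figure.** Protocol 10.5 states margins of about 7% and 6% "if the observed effectiveness rates are 75% and 85%, respectively for low and high doses", with 300 children split evenly (150 per group).

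- 1.96 × √(0.75 × 0.25 / 150) = 6.9%
- 1.96 × √(0.85 × 0.15 / 150) = 5.7%
- Odds ratio (0.85/0.15) / (0.75/0.25) = 1.89, 95% CI 1.06 to 3.38 on the log scale

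The statement reproduces. It concerns precision at the protocol's sample size (the SAP has since reduced the study to about 100 children) and does not say what rate would be seen without a drug effect.

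**2. Model for a child unaffected by the drug.** The untreated time per stage, D, is an assumption: 0.5, 1 or 2 years (182.6, 365.25 or 730.5 days). For elapsed time t, two models for the chance of no advance on one component:

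- child uniformly placed within a stage of fixed length: P = max(0, 1 − t/D)
- constant rate of advance with mean D: P = exp(−t/D)

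Spontaneous regression and staging error are ignored. The SAP does not say whether an advance in one Tanner component or in both counts as progression. If an advance in either of two independent components counts, P is squared. Time is counted as t = 91 for a Day 91 record with baseline near Day 1, and 91 + 93 = 184 with the earliest allowed baseline; counting from Day 1 instead moves results by about one point.

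Example, D = 1 year, t = 91: 1 − 91/365.25 = 75%; exp(−91/365.25) = 78%.

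**3. Chance of scoring as a responder without drug effect** (uniform to exponential model):

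| Record, scoring, baseline | t (days) | D = 0.5 y | D = 1 y | D = 2 y |
|---|---|---|---|---|
| Day 91, one component, near Day 1 | 91 | 50–61% | 75–78% | 88% |
| Day 91, either of two components, near Day 1 | 91 | 25–37% | 56–61% | 77–78% |
| Day 91, one component, 93 days earlier | 184 | 0–37% | 50–60% | 75–78% |
| Day 91, either of two components, 93 days earlier | 184 | 0–13% | 25–37% | 56–60% |
| Day 182, one component, near Day 1 | 182 | 0–37% | 50–61% | 75–78% |
| Day 182, either of two components, near Day 1 | 182 | 0–14% | 25–37% | 56–61% |
| Day 365, one component, near Day 1 | 365 | 0–14% | 0–37% | 50–61% |

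**4. Stage length at which the no-effect rate reaches 50%** (one component, baseline near Day 1). Uniform model: D = 2t. Exponential model: D = t / ln 2.

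- Day 91: about 6.0 or 4.3 months
- Day 182: about 12.0 or 8.6 months
- Day 273: about 18 or 13 months

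**5. End of treatment**, one component, baseline near Day 1, D = 2 years. At 9 months: 1 − 0.75/2 = 63% and exp(−0.375) = 69%. At 36 months: 0% and exp(−1.5) = 22%. At D = 1 year the same pairs are 25–47% and 0–5%.

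**The case against.** The strongest reply is that the size of the effect comes from an assumed tempo, because neither document gives one. That stands, and it rules out the broad reading that an unaffected child would usually score as a responder throughout the early windows. At Day 182 with half a year per stage the figure is 0–37%. At Day 91 it can fall below half under either-component scoring or with an early baseline record. Day 46 is only the edge of the window.

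Several further points also stand:

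- The yearly results are not lost, since Table 1 still contains Months 12, 24, 36, 48 and 60. The protocol made its repeats conditional on the data and left detail to the SAP.
- The primary time point is still end of treatment, in children with at least 9 months of therapy.
- A reader might expect tight Month 3 intervals based on 100 children. The documents do not support that: Tanner records are required only before and at the end of treatment, and results are split by sex. Clopper-Pearson limits are 65–83% for 75/100, but 58–90% for 23/30 and 51–91% for 15/20.
- The protocol's 75% is an assumed rate for the primary variable at end of treatment, so it is not a benchmark for Day 91.
- Tanner response is not the only effectiveness evidence. SAP 7.8.2 and 7.8.3 also report hormone suppression, bone age ratio and predicted adult height.

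None of this answers the core. The rule ignores elapsed time, the 3-month repeats and the missing split are departures from the protocol, and SAP 7.13 declares neither.

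**Conclusion.** The point holds in limited form. At Month 3, with one component and a baseline close to first dose, the no-effect rate is at least about one half over the whole assumed range of 0.5 to 2 years per stage, and 75–78% at 1 year. For Month 6, an early baseline or either-component scoring, it depends on the assumed tempo. A high rate at Month 3, and possibly Month 6, therefore cannot be read as effectiveness.

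The end-of-treatment rate is less exposed, but it mixes children for whom no progression means different things: at 2 years per stage, 63–69% without drug effect at 9 months against 0–22% at 36 months.

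A reader might infer that the endpoint becomes informative at 12 months, so that the conclusion should rest on children treated that long. The documents do not support this. At 2 years per stage the Day 365 figure is still 50–61%. Treatment duration is also known only after baseline, and SAP 7.3 lists lack of efficacy and change to another GnRH agonist among the reasons for stopping, so the longer strata may be selected for responders.

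**What to change.** In SAP 7.8.1 and 7.13:

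1. Restore the protocol's separate percentages and Clopper-Pearson intervals for regression and for no progression, at end of treatment and at each time point reported. This shows how much of the response is a tie without assuming a tempo.
2. For Months 3, 6 and 9, show regressed / same / advanced as descriptive only, not as response to treatment. Keep the combined responder rate for end of treatment and the yearly points.
3. Add a descriptive breakdown of end-of-treatment response by time from the baseline Tanner record to the record used, with bands built from the SAP 7.7 thresholds (for example 9 to <12, 12 to <24, 24 to <36 and ≥36 months). State that the conclusion does not rest on the longer bands.
4. List the change of interval and the dropped sub-response intervals in SAP 7.13, with reasons for any departure kept.

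The cost is SAP wording and a few table rows from data already collected. The downside is small strata with wide intervals, and no favourable early response rate to report.
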